4.5.7.3 Cohort 2 Tumor and Response Evaluations

Patients in Cohort 2 will undergo tumor assessments every 9 (± 1) weeks (from Day 1 of Cycle 1) for the first 54 weeks and then every 12 (± 2) weeks thereafter, regardless of dose delays, as outlined in the schedule of activities (see Section [A14–8](#) [RO7247669 2100 mg + Tira Cohort 2]). The exception is patients who continue treatment after radiographic disease progression. Such patients will undergo tumor assessments every 9 weeks until loss of clinical benefit as determined by the investigator (see Section [3.1.2](#) for details). Thus, tumor assessments are to continue according to schedule in patients who discontinue treatment for reasons other than loss of clinical benefit, even if they start new, non-protocol-specified anti-cancer therapy. Tumor assessments that have been performed outside the protocol-mandated time window do not have to be repeated. However, at the investigator's discretion, tumor assessments may be repeated at any time if progressive disease is suspected.

Brain metastases treated with radiotherapy or surgery will not be considered measurable or evaluable but will be documented at screening as a site of metastatic disease. Brain

metastases identified at baseline that have been treated with radiotherapy or surgery will not be considered measurable or evaluable unless there is suspected disease progression in the brain (i.e., the patient becomes symptomatic). Thus, subsequent head scans are not required unless clinically indicated.

To facilitate evaluation of response per iRECIST in Cohort 2, tumor assessments must be continued after disease progression per RECIST v1.1 for patients who receive treatment beyond progression. This includes continued measurement of target lesions, evaluation of non-target lesions (including monitoring for further worsening of any non-target lesions that have shown unequivocal progression), and evaluation of any newly identified lesions (including measurements, if lesions are measurable; see [Appendix 1](#)) at all subsequent assessments.

Overall response at a single timepoint will be assessed by the investigator using RECIST v1.1 (see [Appendix 1](#)). Assessments should be performed by the same evaluator, if possible, to ensure internal consistency across visits. Available results must be reviewed by the investigator prior to treatment administration.

Overall response per iRECIST (see [Appendix 2](#)) will not be captured in the eCRF, but will instead be calculated programmatically by the Sponsor on the basis of investigator-assessed individual lesion data recorded in the eCRF.

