4.6 TREATMENT, PATIENT, STUDY, AND SITE DISCONTINUATION

4.6.1 Study Treatment Discontinuation

Patients must permanently discontinue study treatment if they experience any of the following:

- Intolerable toxicity related to study treatment, including development of an immune-mediated adverse event determined by the investigator to be unacceptable given the individual patient's potential response to therapy and severity of the event
- Any medical condition that may jeopardize the patient's safety if he or she continues study treatment
- Investigator or Sponsor determines it is in the best interest of the patient
- Use of another non-protocol-specified anti-cancer therapy
- Pregnancy
- Cohort 1: Confirmed disease progression or dissemination prior to surgery. Patients who discontinue study treatment early because of an unacceptable toxicity should continue to be followed for both resolution of toxicity and disease recurrence as outlined in the schedule of activities (Sections [A11–6](#) [Nivo+Ipi], [A12–6](#) [RO7247669 2100 mg], [A13–6](#) [Atezo+Tira], [A14–6](#) [RO7247669 2100 mg +Tira Cohort 1], [A15–6](#) [RO7247669 600 mg], and [A16–6](#) [RO7247669 600 mg +Tira]).
- Cohort 2: Loss of clinical benefit as determined by the investigator after an integrated assessment of radiographic and biochemical data, local biopsy results (if available), and clinical status (e.g., symptomatic deterioration such as pain secondary to disease) (see Section [3.1.2](#) for details)

The primary reason for study treatment discontinuation should be documented on the appropriate eCRF.

For Cohort 1, regardless of whether they complete the study drug treatment period or discontinue study drug prematurely, patients who proceed to surgery will return to the clinic for a treatment completion/discontinuation visit 6 weeks after surgery and patients who do not proceed to surgery will return to the clinic for a treatment completion/discontinuation visit not more than 30 days after the final dose of study treatment. For patients who progress or have loss of clinical benefit, the visit at which response assessment shows progressive disease or loss of clinical benefit may be used as the treatment discontinuation visit.

For Cohort 2, patients who discontinue study treatment for any reason other than progressive disease or loss of clinical benefit will continue to undergo tumor response assessments as outlined in the schedule of activities (see [A14-8](#)).

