5.3.5.10 Lack of Efficacy or Worsening of Melanoma

Events that are clearly consistent with the expected pattern of progression of the underlying disease should not be recorded as adverse events. These data will be captured as efficacy assessment data only. In most cases, the expected pattern of progression will be based on RECIST v1.1. In rare cases, the determination of clinical progression will be based on symptomatic deterioration. However, every effort should be made to document progression through use of objective criteria. If there is any uncertainty as to whether an event is due to disease progression, it should be reported as an adverse event.

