The ORR according to RECIST v1.1 will be assessed after completion of neoadjuvant treatment (Week 7) and is defined as the proportion of patients with a CR or PR, as determined by the investigator according to RECIST v1.1. Patients with missing or no response assessments will be classified as non-responders. Note that ORR will be determined using unconfirmed pre-operative radiologic responses. Although RECIST v1.1 requires confirmatory imaging assessments to be completed at least 4 weeks after the initial response, due to the timing of CLND, these responses cannot be confirmed with subsequent imaging.

ORR will be calculated for each arm, along with 95% CIs (Clopper-Pearson method). The difference in ORR between the experimental arms and the control arm will also be calculated, along with 95% CIs using the Wald method with continuity correction.

6.4.3 Exploratory Efficacy Endpoints in Cohort 1

The exploratory efficacy endpoints in Cohort 1 are landmark EFS, landmark RFS, and landmark OS at specific timepoints (1, 2, 3, and 5 years). RFS, EFS, and OS are defined in Section [6.4.2](#).

Landmark EFS rates, landmark RFS rates, and landmark OS rates will be estimated for each study arm using the Kaplan-Meier method, with 95% CIs calculated through use of Greenwood's formula.

6.4.4 Primary Efficacy Endpoint in Cohort 2

The primary efficacy endpoint in Cohort 2 is ORR, as defined in Section [2](#) (see [Table 3](#)). ORR is determined by the investigator according to RECIST v1.1. Patients with missing or no response assessments will be classified as non-responders.

ORR, the proportion of patients with a complete or partial response, will be calculated for each arm, along with 95% CIs (Clopper-Pearson method).

6.4.5 Secondary Efficacy Endpoints in Cohort 2

The secondary efficacy endpoints in Cohort 2 are PFS, OS, OS at specific timepoints (e.g., 6 months), duration of response (DOR), and disease control, as defined in Section [2](#) (see [Table 3](#)). PFS, DOR, and disease control are determined by the investigator according to RECIST v1.1.

DOR will be derived for efficacy-evaluable patients with a CR or PR.

For patients who do not have documented disease progression or death, PFS and DOR will be censored at the day of the last tumor assessment.

Patients who are still alive at the time of OS analysis will be censored at the last date they were known to be alive.

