Appendix 1: Response Evaluation Criteria in Solid Tumors, Version 1.1 (RECIST v1.1)

having "symptomatic deterioration." Every effort should be made to document objective progression even after discontinuation of treatment. Symptomatic deterioration is not a descriptor of an objective response; it is a reason for stopping study therapy. The objective response status of such patients is to be determined by evaluation of target and non-target lesions as shown in [Table A1-1](#).

For equivocal findings of progression (e.g., very small and uncertain new lesions; cystic changes or necrosis in existing lesions), treatment may continue until the next scheduled assessment. If at the next scheduled assessment, progression is confirmed, the date of progression should be the earlier date when progression was suspected.

A1-5 REFERENCES

Appendix 2
Modified RECIST v1.1 for Immune-Based Therapeutics (iRECIST)

TABLE OF CONTENTS

A2-1	Modified RECIST v1.1 for Immune-Based Therapeutics (iRECIST).....	126
A2-1.1	Evaluation of Lesions to Support iRECIST Response	
	Assessment after Disease Progression per RECIST v1.1	126
A2-1.1.1	Target Lesions	127
A2-1.1.2	Non-Target Lesions	127
A2-1.1.3	New Lesions	127
A2-1.2	Summary of Criteria for Overall Response at a Single Timepoint	128
A2-2	References.....	129

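### Cohort 2: scheduled scans end at loss of clinical benefit, which is not itself a PFS event, so such failures may be censored or counted only at death, biasing PFS upward

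*Combined protocol and SAP*

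**What the plan says.** - **Section 4.5.7.3** sets Cohort 2 scans every 9 weeks to Week 54 and every 12 weeks after that. Once treatment stops, "tumor assessments are to continue according to schedule in patients who discontinue treatment for reasons other than loss of clinical benefit", and this applies even after another anti-cancer therapy has begun. Patients treated past radiographic progression have their own rule: "Such patients will undergo tumor assessments every 9 weeks until loss of clinical benefit as determined by the investigator". The section also says that "tumor assessments may be repeated at any time if progressive disease is suspected".
- **Section 4.6.1** says that "patients who discontinue study treatment for any reason other than progressive disease or loss of clinical benefit will continue to undergo tumor response assessments". Among the reasons for stopping it lists "Loss of clinical benefit as determined by the investigator after an integrated assessment of radiographic and biochemical data", together with biopsy results and clinical status, with pain from the disease as an example. RECIST progression is not a condition. The primary reason for stopping goes on the eCRF.
- **Section 5.3.5.10**, on adverse event recording, says: "In rare cases, the determination of clinical progression will be based on symptomatic deterioration". Its next sentence asks sites to use objective criteria to document progression wherever they can.
- **Appendix 1, A1-4.7** treats symptomatic deterioration as a reason to stop therapy and not as an objective response category. It adds: "Every effort should be made to document objective progression even after discontinuation of treatment".
- **Table 3 and Section 6.4.5** define PFS as investigator-assessed RECIST v1.1 progression or death. "For patients who do not have documented disease progression or death, PFS and DOR will be censored at the day of the last tumor assessment". Section 6.4.5 does not mention loss of clinical benefit.
- **Section 6.9** names PFS and duration of response among the data that may inform a decision to expand an arm.

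**The concern.** The required scan schedule continues for a patient who stops for toxicity, or who moves to another therapy, but not for a patient whom the investigator judges to be failing. If that judgment comes before RECIST progression, the analysis may have nothing to record as progression. The patient then leaves the risk set because of a poor prognosis, which breaks the independent-censoring assumption of Kaplan-Meier in a known direction. Cohort 2 has a single arm, so no control group shares the bias, and PFS is one of the inputs to the expansion decision.

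**Working it through.** **1. Who is affected.** Patients treated beyond RECIST progression already have their PFS event. The affected group is those who lose clinical benefit before any RECIST progression and have no later scan. Under Section 6.4.5 each is either an event at death or, if alive at the cut, censored at the last scan before deterioration. If deterioration comes before the Week 9 scan, that last scan is the baseline one.

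**2. Direction.** Suppose first failures occur at constant hazard λ and a share f is censored when it happens. Kaplan-Meier then estimates hazard (1 − f)λ, so the median is multiplied by 1/(1 − f): 1.05, 1.11 and 1.25 for f = 5%, 10% and 20%. This simple case ignores the scan grid and later deaths.

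**3. Size: inputs.** The documents give no PFS assumption, event count or power for Cohort 2, so there is no figure of theirs to reproduce. Only the scan grid comes from the plan. The rest is assumed: exponential times, f of 5% to 20%, and two sets of medians.
- Set A: median time to progression/median time from progression to death of 10/13, 10/26, 10/40 and 16/13 weeks; data cut uniform over 26 to 78 weeks.
- Set B: 12/8, 12/17, 20/8 and 20/17 weeks; 104 weeks of follow-up.

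PFS under the plan's rules with no further scans was compared with (i) continued scanning, where progression is found at the next scheduled scan, and (ii) deterioration counted as an event on its own date.

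**4. Size: results.** Increase in week-26 PFS, in percentage points:

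| Share f | (i) Set A | (i) Set B | (ii) Set A | (ii) Set B |
|---|---|---|---|---|
| 5% | 0.9–1.5 | 0.6–1.6 | 1.4–2.1 | 1.0–2.1 |
| 10% | 1.8–3.1 | 1.1–3.0 | 2.8–4.3 | 2.0–4.1 |
| 20% | 3.6–6.4 | 2.1–6.1 | 5.6–8.7 | 4.0–8.3 |

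Example (Set B, 12/17, f = 10%): (i) 0.364 − 0.334 = 0.030; (ii) 0.364 − 0.323 = 0.041. If half of the affected patients do get a scan, the gap under (i) roughly halves.

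**5. Median.** Most events fall on scan dates, so the median often stays put.
- Set A, 10-week median, f = 20%: 18 weeks under the plan's rules. Continued scanning also gives 18 when median survival after progression is 26 or 40 weeks, and about 16 when it is 13. Counting deterioration as an event gives 13 to 14.
- Set A, 16/13: plan and continued scanning agree at 18 weeks for f = 5% and 10%; at 20% they are about 21.5 and 18.
- Set B: 12/8 and 12/17 give 18 weeks under both at every f shown, and 20/17 gives 27 under both. At 20/8 the median rises by about a week (25.7 to 26.9 at f = 10%).

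**6. Scale.** The upper size is 6 + 20 + 20 = 46. Shares of 5%, 10% and 20% of 46 are 2.3, 4.6 and 9.2 patients; of the lower size, 8, they are 0.4, 0.8 and 1.6. After run-in plus preliminary phase (6 + 20 = 26), the standard error of a PFS proportion is √(0.25 × 0.75/26) = 8.5 points at 25% and √(0.43 × 0.57/26) = 9.7 points at 43%.

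**The case against.** **A reader might infer that the plan sets two contradictory stopping points for scans.** It does not. A1-4.7 is a best-effort instruction with no schedule, Section 5.3.5.10 points the same way, and Section 4.5.7.3 permits a scan whenever progression is suspected. A site can follow all of them. What remains is a tension: the required schedule lapses for the group in which objective documentation is most wanted, so ascertainment depends on site discretion. There is one plain mismatch. Section 4.6.1 also ends scans at progressive disease and Section 4.5.7.3 does not. That bears mainly on the iRECIST endpoints, because RECIST progression is already the PFS event.

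**A reader might also infer that PFS is overstated as a matter of fact, or that the median would be reported several weeks too long.** The documents do not support either. The affected share is unknown, and the only hint calls clinical progression rare. The large median shift (13 to 14 weeks against 18) arises mainly from comparing the plan with deterioration dated as an event; against continued scanning most or all of it disappears. Week-26 PFS is an illustration chosen here: for Cohort 2 PFS the plan reports a median, and Week 26 falls just before the Week 27 scan (3 × 9).

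**The consequences are limited.** PFS is secondary, there is no hypothesis test, the expansion rule illustrated for Cohort 2 uses ORR, and no Cohort 2 arm is open. At a 5% or 10% share the bias is well below the sampling error. All of this stands and limits the weight of the point. It does not fill the gap in Section 6.4.5, and the enrolled patients' PFS and DOR will still be reported.

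**Conclusion.** The point holds as a gap in the analysis rules. A Cohort 2 patient who stops for loss of clinical benefit before RECIST progression, and is not scanned again, is censored at the last assessment or counted only at death. The resulting bias in PFS is upward; every scenario tried agreed on direction. Its size rests on assumed survival times and an assumed share. Across both sets, against continued scanning, it runs from 0.6 points of week-26 PFS (5% share) to about 6 points (20%), usually with little or no change in the median. Against counting deterioration as an event, it runs from 1.0 to 8.7 points over the same shares. DOR uses the same censoring rule, so the same direction applies in principle, but no DOR figure was computed. The Cohort 2 schedule of activities (A14-8), to which Sections 4.5.7.3 and 4.6.1 both refer, was not in the text available and could resolve part of the tension. The change is worth making because it is cheap and the bias has a known direction, but it does not threaten the study's main conclusions.

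**What to change.** - **Section 6.4.5:** keep the RECIST v1.1 analyses unchanged as the main ones. Add a supplementary PFS and DOR analysis in which treatment discontinuation for loss of clinical benefit, without prior RECIST progression, is an event on the discontinuation date. Report the two side by side, with the number of patients reclassified.
- **Sections 4.5.7.3, 4.6.1, 5.3.5.10 and A1-4.7:** reconcile what they say about tumor assessment follow-up for these patients, including the differing treatment of progressive disease in 4.5.7.3 and 4.6.1, and check A14-8 against the result. How these patients should be imaged is for the sponsor and investigators to settle.

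The cost is a few lines of text and one further Kaplan-Meier run each for PFS and DOR. Section 4.6.1 already puts the primary discontinuation reason on the eCRF. The text describes no separate date for loss of benefit, so the rule should name the discontinuation date and the sponsor should confirm that it is captured. The drawbacks are some investigator subjectivity in the added event and a slightly less favourable supplementary PFS.

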4.5.8 Classification of Surgical Complications

Surgical complications will be scored according to Clavien-Dindo classification ([Appendix 5](#)). Complication rates for every grade will be reported and scored for patients that underwent CLND, as outlined for each arm in the schedules of activities (see Sections [A11–6](#) [Nivo + Ipi], [A12–6](#) [RO7247669 2100 mg], [A13–6](#) [Atezo + Tira], [A14–6](#) [RO7247669 2100 mg + Tira Cohort 1], [A15–6](#) [RO7247669 600 mg], and [A16–6](#) [RO7247669 600 mg + Tira]).

4.5.9 Laboratory, Biomarker, and Other Biological Samples

4.5.9.1 Local Laboratory Assessments

For information about the timing of local laboratory assessments, please refer to the schedule of activities for screening ([Appendix 10](#)) or the appropriate treatment arm (Sections [A11–6](#) [Nivo + Ipi], [A12–6](#) [RO7247669 2100 mg], [A13–6](#) [Atezo + Tira], [A14–6](#) [RO7247669 2100 mg + Tira Cohort 1], [A14–8](#) [RO7247669 2100 mg + Tira Cohort 2], [A15–6](#) [RO7247669 600 mg], and [A16–6](#) [RO7247669 600 mg + Tira]).

Samples for the following laboratory tests will be sent to the study site's local laboratory for analysis:

- Hematology: WBC count, RBC count, hemoglobin, hematocrit, platelet count, and differential count (neutrophils, eosinophils, basophils, monocytes, lymphocytes, and other cells)

- Chemistry panel (serum or plasma): includes sodium, potassium, magnesium, chloride, bicarbonate or total carbon dioxide (if considered standard of care in the region), glucose, BUN or urea, creatinine, total protein, ferritin, albumin, phosphate, calcium, total bilirubin, ALP, ALT, AST, amylase, lipase, and LDH. In addition, adrenocorticotrophic hormone (ACTH), cortisol, S100, and erythrocyte sedimentation rate (ESR) will be assessed at screening and pre-surgery visits for patients enrolled in Cohort 1.
- Lipid panel: includes triglycerides, HDL, and LDL
- Coagulation: INR and aPTT
- Thyroid function testing: TSH, free T3 (or total T3 for sites where free T3 is not performed), and free T4
- Cardiac enzymes: troponin I or T
- C-reactive protein
- HIV serology, unless not permitted per local regulations
- HBV serology: hepatitis B surface antigen (HBsAg), hepatitis B surface antibody (HBsAb), total hepatitis B core antibody (HBcAb), and (if HBsAg test is negative and total HBcAb test is positive) HBV DNA

If a patient has a negative HBsAg test and a positive total HBcAb test at screening, an HBV DNA test must also be performed to determine if the patient has an HBV infection.
- HCV serology: HCV antibody and (if HCV antibody test is positive) HCV RNA

If a patient has a positive HCV antibody test at screening, an HCV RNA test must also be performed to determine if the patient has an HCV infection.
- EBV serology:
 - EBV VCA IgM
 - EBV VCA IgG or Epstein-Barr nuclear antigen (EBNA) IgG
 - EBV PCR (only if clinically indicated)
- Cytomegalovirus (CMV) serology: CMV IgM and IgG

If a patient has a positive CMV IgM test or $\geq 4 \times$ ULN increase in CMV IgG, quantitative PCR should be used to determine if the patient has a CMV infection.
- Pregnancy test

All women of childbearing potential will have a serum pregnancy test at screening. Urine or serum pregnancy tests will be performed at specified subsequent visits. If a urine pregnancy test is positive, it must be confirmed by a serum pregnancy test. Pregnancy tests will also be performed at treatment completion/discontinuation at Week 13 and during follow-up at 6 months in Cohort 1, and at 3 and 6 months in Cohort 2.

A woman is considered to be of childbearing potential if she is postmenarcheal, has not reached a postmenopausal state (≥ 12 continuous months of amenorrhea with no identified cause other than menopause), and is not permanently infertile due to surgery (i.e., removal of ovaries, fallopian tubes, and/or uterus) or another cause as determined by the investigator (e.g., Müllerian agenesis).

- Urinalysis (pH, specific gravity, glucose, protein, ketones, and blood); dipstick permitted

4.5.9.2 Central Laboratory Assessments

For information about the timing of central laboratory assessments, please refer to the schedule of activities for screening ([Appendix 10](#)) or the appropriate treatment arm (Sections [A11–6](#) [Nivo + Ipi], [A12–6](#) [RO7247669 2100 mg], [A13–6](#) [Atezo + Tira], [A14–6](#) [RO7247669 2100 mg + Tira Cohort 1], [A14–8](#) [RO7247669 2100 mg + Tira Cohort 2], [A15–6](#) [RO7247669 600 mg], and [A16–6](#) [RO7247669 600 mg + Tira]).

The following samples will be sent to one or several central laboratories or to the Sponsor or a designee for analysis:

- Serum sample for analysis of autoantibodies: anti–nuclear antibody, anti–double-stranded DNA, circulating anti–neutrophil cytoplasmic antibody, and perinuclear anti–neutrophil cytoplasmic antibody
- Serum samples for PK analysis through use of validated assays
- Serum samples for immunogenicity analysis through use of validated assays
- Plasma and blood for exploratory research on biomarkers including blood-based NGS/WES ctDNA assay to determine tumor-specific alterations
- Archival tumor tissue sample for exploratory research on biomarkers

An archival primary tumor tissue sample, preferably as a FFPE tumor tissue block with representation and sufficient tumor content, including the invasive margin (preferred), or, if available, at least 16 slides containing unstained, freshly cut, serial sections, must be submitted along with an associated pathology report. For the Cohort 2 safety run-in phase, submission of an archival sample is preferred, but patients are eligible for the study if no archival sample is available. Remaining archival tumor tissue blocks will be returned to the site upon request or 18 months after final closure of the study database, whichever occurs first.

- Fresh baseline and on-treatment tumor tissue for exploratory research on biomarkers

Baseline tumor tissue samples will be collected from all patients (except patients in the Cohort 2 safety run-in phase) by biopsy of a metastatic lymph node (Cohort 1) or other metastatic lesion (Cohort 2) at screening. For patients in Cohort 1, on-treatment tissue samples will be collected by biopsy on Day 1 of Cycle 2 (up to 72 hours prior to drug administration), and at surgery (CLND). For patients enrolled in Cohort 2, on-treatment tissue samples will be collected

by biopsy on Day 8 of Cycle 2. An overview of planned tissue samples is provided in [Table 6](#).

To mitigate potential risk associated with tumor biopsies, all patients undergoing fresh tumor biopsies must have tumor lesions from which biopsies can be safely obtained, as per clinical judgment of the treating physician. Collection of tumor biopsies should be guided by ultrasound, CT scan or other methods according to the location of the selected lesion. Collect at least 3 cores (preferably 4 cores) using a 14-gauge needle, ideally of at least 20 mm in length or equivalent size. Fresh tumor tissue will be processed as described in the laboratory manual .

The baseline and on-treatment biopsies should preferably be taken from the same tumor lesion/metastasis to ensure comparability. If the lesion biopsied at baseline cannot be biopsied on treatment (e.g., because lesion is no longer present or can no longer be safely biopsied), then an alternative lesion should be biopsied. Preferably the new lesion would be in a similar tissue. If feasible, biopsies may be repeated if the initial biopsy did not contain sufficient tumor material for analysis. The location of each biopsy will be documented in relation to each tumor lesion as determined by imaging.

Table 6 Overview of Mandatory Tissue Samples

Timepoint	Sample Type	Requirement
Cohort 1		
Screening	Archival tissue	Mandatory (if available)
Screening	Fresh biopsy	Mandatory
Cycle 2 Day 1 (up to 72 hours prior to drug administration)	Fresh biopsy	Mandatory
Surgery (CLND) Week 7	Fresh tissue from surgery	Mandatory
Cohort 2 (except safety run-in)		
Screening	Archival tissue	Mandatory (if available)
Screening	Fresh biopsy	Mandatory
Cycle 2 Day 8	Fresh biopsy	Mandatory

CLND = complete lymph node dissection

Tumor tissue should be of good quality based on total and viable tumor content. Samples must contain a minimum of two consecutive high power fields of viable tumor, if possible including the invasive margin that preserves cellular context and tissue architecture, regardless of needle gauge or retrieval method. Samples collected via resection, core-needle biopsy, or excisional, incisional, punch biopsy are acceptable. Fine-needle aspiration (defined as samples that do not preserve tissue architecture and yield cell suspension and/or smears), brushing, cell pellets from pleural effusion, and

lavage samples are not acceptable. Tumor tissue from bone metastases that have been decalcified is not acceptable.

Exploratory biomarker research may include, but will not be limited to, analysis of genes or gene signatures associated with tumor immunobiology, PD-L1, lymphocyte subpopulations *and their functional and/or activation status*, T-cell receptor repertoire, or cytokines associated with T-cell activation. Research may involve extraction of DNA, cell-free DNA, or RNA; analysis of mutations, single nucleotide polymorphisms, and other genomic variants; and genomic profiling through use of NGS of a comprehensive panel of genes. DNA extracted from blood may be compared with DNA extracted from tissue to identify somatic variants by distinguishing germline variants from somatic variants. NGS methods may include whole genome sequencing (WGS) or WES of tissue and blood samples, but WGS or WES of blood samples will be performed only at participating sites (see Section [4.5.10](#)).

For sampling procedures, storage conditions, and shipment instructions, see the laboratory manual.

Unless the patient gives specific consent for his or her leftover samples to be stored for optional exploratory research (see Section [4.5.12](#)), biologic samples will be destroyed no later than the time of completion of the final Clinical Study Report (CSR), with the following exceptions:

- Serum and plasma samples collected for PK analysis or immunogenicity analysis may be needed for additional immunogenicity characterization and PK and immunogenicity assay development and validation; therefore, these samples will be destroyed no later than 5 years after the final CSR has been completed.
- Blood, plasma, peripheral blood mononuclear cell (PBMC), and tumor tissue collected for biomarker research will be destroyed no later than 5 years after the final CSR has been completed, with the exception of the samples that undergo WES, which will be stored until they are no longer needed or until they are exhausted. However, the storage period for the WES samples will be in accordance with the Institutional Review Board (IRB)/Ethics Committee (EC)-approved Informed Consent Form and applicable laws (e.g., health authority requirements).
- For enrolled patients, remaining archival tissue blocks will be returned to the site upon request or no later than the time of final closure of the study database, whichever occurs first. For patients who are not enrolled, remaining archival tissue blocks will be returned to the site no later than 6 weeks after eligibility determination.

When a patient withdraws from the study, samples collected prior to the date of withdrawal may still be analyzed, unless the patient specifically requests that the samples be destroyed or local laws require destruction of the samples. However, if samples have been tested prior to withdrawal, results from those tests will remain as part of the overall research data.

Data arising from sample analysis will be subject to the confidentiality standards described in Section 8.4.

Given the complexity and exploratory nature of biomarker analyses, data derived from these analyses will generally not be provided to study investigators or patients unless required by law. The aggregate results of any conducted research will be available in accordance with the effective Sponsor policy on study data publication.

4.5.10 Blood Samples for Whole Genome Sequencing or Whole Exome Sequencing (Patients at Participating Sites)

At participating sites, blood samples will be collected for DNA extraction to enable WGS or WES to identify variants that are predictive of response to study drug, are associated with progression to a more severe disease state, are associated with acquired resistance to study drug, are associated with susceptibility to develop adverse events, can lead to improved adverse event monitoring or investigation, or can increase the knowledge and understanding of disease biology and drug safety. DNA extracted from blood may be compared with DNA extracted from tissue to identify somatic variants by distinguishing germline variants from somatic variants. The samples may be sent to one or more laboratories for analysis.

Collection and submission of blood samples for WGS or WES is contingent upon the review and approval of the exploratory research by each site's IRB/EC and, if applicable, an appropriate regulatory body. If a site has not been granted approval for WGS or WES, this section of the protocol (Section 4.5.10) will not be applicable at that site.

Genomics is increasingly informing researcher's understanding of disease pathobiology. WGS and WES provide a comprehensive characterization of the genome and exome, respectively, and, along with clinical data collected in this study, may increase the opportunity for developing new therapeutic approaches or new methods for monitoring efficacy and safety or predicting which patients are more likely to respond to a drug or develop adverse events. Data will be analyzed in the context of this study but may also be explored in aggregate with data from other studies. The availability of a larger dataset will assist in identification and characterization of important biomarkers and pathways to support future drug development.

For sampling procedures, storage conditions, and shipment instructions, see the laboratory manual.

Blood samples collected for WGS or WES are to be stored until they are no longer needed or until they are exhausted. However, the storage period will be in accordance with the IRB/EC-approved Informed Consent Form and applicable laws (e.g., health authority requirements).

Refer to Section 4.5.9 for details on use of samples after patient withdrawal, confidentiality standards for data, and availability of data from biomarker analyses.

